6.1.3.2 Lack of Efficacy or Worsening of Disease

Events that are clearly consistent with the expected pattern of progression of the underlying disease are also considered an expected outcome for this study and will not be subject to expedited reporting.

6.1.4 Relationship to Study Drug

The investigator will use the following definitions to assess the relationship of the adverse event to the use of study drug:

Reasonable Possibility	After consideration of factors including timing of the event, biologic plausibility, clinical judgment, and potential alternative causes, there is sufficient evidence (information) to suggest a causal relationship.
No Reasonable Possibility	After consideration of factors including timing of the event, biologic plausibility, clinical judgment, and potential alternative causes, there is insufficient evidence (information) to suggest a causal relationship.

For causality assessments, events assessed as having a reasonable possibility of being related to the study drug will be considered "associated." Events assessed as having no reasonable possibility of being related to study drug will be considered "not associated." In addition, when the investigator has not reported causality or deemed it not assessable, AbbVie will consider the event associated.

If an investigator's opinion of no reasonable possibility of being related to study drug is given, an "Other" cause of event must be provided by the investigator for the serious adverse event.

6.1.5 Adverse Event Collection Period

[figure not shown]
All protocol-related serious adverse events and nonserious adverse events must be collected from the signing of the study specific informed consent until study drug administration.

Serious and nonserious adverse events occurring after the study-specific informed consent is signed but prior to the initial dose of study drug will be collected only if they are considered by the investigator to be causally related to the study-required procedures.

In addition, all serious and nonserious adverse events reported from the time of study drug administration until 30 days following discontinuation of study drug administration have elapsed will be collected, whether solicited or spontaneously reported by the subject.

Adverse event information will be collected as shown in [Figure 11](#).

Figure 11. Adverse Event Collection

* Only if considered by the investigator to be causally related to study required procedures.

6.1.6 Adverse Event Reporting

In the event of a serious adverse event, whether associated with study drug or not, the investigator will notify Clinical Pharmacovigilance within 24 hours of the site being made aware of the serious adverse event by entering the serious adverse event data into the electronic data capture (EDC) system. Serious adverse events that occur prior to the site having access to the RAVE[®] system or if RAVE is not operable should be documented on the SAE Non-CRF forms and emailed (preferred route) or faxed to Clinical Pharmacovigilance within 24 hours of the site or investigator being made aware of the serious adverse event.

FAX to: [contact]
Email: [contact]

For safety concerns, contact the Oncology Safety Management Team at:

Oncology Safety Management
[name]
AbbVie
[name]
[name]

Safety [contact]
Safety Email: [contact]

For any subject safety concerns, please contact the physician listed below:

Primary Study Designated Physician:

[REDACTED]
Clinical Oncology
AbbVie
[REDACTED]
[name]
[name]

Phone: [REDACTED]
Fax: [REDACTED]

In emergency situations involving study subjects when the primary Study Designated Physician (SDP) is not available by phone, please contact the 24-hour **AbbVie Medical Escalation Hotline** where your call will be re-directed to a designated AbbVie SDP.

[contact]

The sponsor will be responsible for Suspected Unexpected Serious Adverse Reactions (SUSAR) reporting for the Investigational Medicinal Product (IMP) in accordance with Directive 2001/20/EC. The reference document used for SUSAR reporting in the EU

countries will be the most current version of the Investigator's Brochure or Summary of Product Characteristics (SmPC) for cytarabine.

COVID-19 Pandemic-Related Acceptable Protocol Modifications

Supplemental study case report forms should be completed in the event of COVID-19 related missed/virtual visits, study drug interruptions or discontinuations, or adverse events (including capture of specific signs/symptoms of infection and testing results).

COVID-19 infections should be captured as adverse events. If the event meets the criteria for a serious adverse event (SAE), then follow the SAE reporting directions per the protocol and above. The following COVID-19 related supplemental eCRFs should be completed (for both serious and non-serious events):

- COVID -19 Supplemental Signs/ Symptoms
- COVID-19 Status Form

6.1.7 Pregnancy

Pregnancy in a study subject must be reported to an AbbVie representative (Section 6.1.6 or Section 7.0) within 1 working day of the site becoming aware of the pregnancy. Subjects who become pregnant during the study must be discontinued (Section 5.4.1).

All subjects should be informed that contraceptive measures should be taken throughout the study and for 180 days after discontinuing study drug. Male subjects should be informed that contraceptive measures should be taken by their female partner. Information regarding a pregnancy occurrence in a study subject and the outcome of the pregnancy will be collected. In the event of pregnancy occurring in the partner of an enrolled subject, written informed consent for release of medical information from the partner must be obtained prior to the collection of any pregnancy-specific information and the pregnancy will be followed to outcome.

Information regarding a pregnancy occurrence in a study subject and the outcome of the pregnancy will be collected.

Pregnancy in a study subject is not considered an adverse event. However, the medical outcome of an elective or spontaneous abortion, stillbirth or congenital anomaly is considered a serious adverse event and must be reported to AbbVie within 24 hours of the site becoming aware of the event.

6.1.8 Toxicity Management

6.1.8.1 Definition – Dose Limiting Toxicity

Dose limiting toxicities (DLTs) for dose-escalation purposes will be determined during Cycle 1 (4 weeks) of study treatment. Adverse events that occur after the first cycle will also be evaluated by the investigator and the AbbVie medical monitor and may be considered as dose limiting.

Any of the following events, which cannot be attributed by the investigator to a clearly identifiable cause such as tumor progression, underlying illness, concurrent illness, or concomitant medication, will be considered a DLT:

- Grade 4 or 5 non-hematologic toxicity considered at least possibly related to the study drug, except those listed in [Appendix F](#).
- Grade 4 or 5 pancytopenia with a hypocellular bone marrow and no greater than or equal to 5% marrow blasts lasting for 42 days or more.

Any DLT will require an interruption and possible discontinuation of venetoclax or LDC. Venetoclax and LDC therapy may be reintroduced at a reduced dose, if the toxicity grade returns to \leq Grade 1 or to baseline if Grade 2 at study entry.

Any reduced dose level will be jointly defined by the investigator and the AbbVie medical monitor. The dose may be increased thereafter upon joint determination of the investigator and the AbbVie medical monitor. This dose is not to exceed the highest tolerated dose level. All decisions regarding continued dosing for individual subjects will

be medically managed by the investigator, per discussion with the AbbVie medical monitor, as appropriate. These decisions will be driven by the definition of DLTs as described above.

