For this trial, DLTs are defined as experiencing a CTCAE grade 4 toxicity, unless such events are in the common list of health events due to AML ([Appendix F](#)), or not recovering platelets to at least $25,000/\mu\text{L}$ and ANC to $500/\mu\text{L}$ within 14 days of the last dose of venetoclax unless such cytopenias are due to residual leukemia effect. Should 1 subject experience a DLT, an additional 3 subjects will be enrolled at the same dose level (a total of 6 subjects at this dose level). Should 2 subjects at a dose level experience a DLT, that dose level is considered too toxic. The dose level below the too toxic dose level is considered the MTD. Additional subjects are then enrolled at the MTD to bring the total number enrolled at the MTD to 6. If during this cohort expansion, a total of 2 subjects at this dose level also experience a DLT, this level would also be considered too toxic and the method continues thusly until the maximal dose level is achieved where 6 subjects can be treated through Cycle 1 and no more than one subject experiences a DLT. Additional subjects may be enrolled at the current dose level at the discretion of the AbbVie medical monitor, if enrolled subjects are not evaluable. In addition, significant

adverse events occurring after Cycle 1 in previous dose levels and ongoing PK assessments may inform dose escalation decisions and should such unanticipated occurrences necessitate a modification to the planned cohort dose assignments, decisions will be communicated in writing to all investigators.

Dose Escalation Guidelines

Number of Subjects with DLT	Dose Escalation
0 of 3	Begin enrollment in the next dose level
1 of 3	Enroll 6 subjects in current dose level
1 of 6 or < 33% DLTs	Begin enrollment in the next dose level
≥ 2 of 6 or ≥ 33% DLTs	Previous dose determined as the MTD or dose de-escalation

If a dose de-escalation occurs and < 33% of subjects enrolled experience a DLT at the reduced designated cohort dose, this dosing regimen will be declared the MTD. If ≥ 33% of the subjects enrolled at the reduced designated cohort dose still experience a DLT, dose de-escalation of the designated cohort dose regimen will continue to be explored.

The MTD will be defined as the highest designated cohort dose level (and corresponding ramp-up period regimen, if applicable) at which < 33% of the subjects enrolled experience a DLT.

[figure not shown]

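### The protocol gives conflicting DLT definitions without saying which governs, and neither hematologic rule fits the 4-week DLT window as written

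*Protocol*

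**What the plan says.** Three places in the protocol define a DLT.

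- **Section 1.2 (Synopsis)** counts a grade 4 or 5 toxicity that is not on the list of events common in AML. It also counts failure to recover platelets to 25,000/µL and ANC to 500/µL within 14 days of the last venetoclax dose, unless residual leukemia explains it.
- **Section 5.1** repeats this but names only grade 4: "For this trial, DLTs are defined as experiencing a CTCAE grade 4 toxicity, unless such events are in the common list of health events". Its recovery clause runs "within 14 days of the last dose of venetoclax unless such cytopenias are due to residual leukemia effect". This text stands just above the dose escalation table.
- **Section 6.1.8.1** says that DLTs for dose-escalation purposes "will be determined during Cycle 1 (4 weeks) of study treatment". It counts "Grade 4 or 5 non-hematologic toxicity considered at least possibly related to the study drug", outside Appendix F, and only events "which cannot be attributed by the investigator to a clearly identifiable cause". Its hematologic criterion is grade 4 or 5 pancytopenia with a hypocellular marrow and "no greater than or equal to 5% marrow blasts lasting for 42 days or more". Later events are reviewed by the investigator "and the AbbVie medical monitor and may be considered as dose limiting".

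Section 5.1 places the escalation decision typically 28 ± 14 days after the last subject in a cohort starts. A subject is evaluable after a DLT and/or at least 80% of Cycle 1 dosing. Under Sections 5.1 and 6.1.8.6 a dose level clears with fewer than 2 DLTs in 6, or below 33% in a larger cohort. If an MTD is reached, Section 6.1.8.7 does not let the RPTD exceed it.

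**The concern.** Determining the MTD is a Phase 1 primary objective, and the rule that produces it counts DLTs in very small cohorts. If two sections of the same protocol classify the same subject differently, a reported DLT count or MTD can be read only by someone who knows which section was used.

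For this study the SAPs list only 600 mg and 800 mg, and the Phase 2 schema is 600 mg. The practical question is therefore whether 800 mg exceeded the MTD or 600 mg was chosen on other grounds.

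The analysis plan does not settle the definition. Protocol Section 8.1.4 describes no DLT analysis. The event list in Section 7.6.1 of the safety SAP, which is open-ended, does not name one.

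**Working it through.** **1. The definitions side by side**

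| Element | 1.2 | 5.1 | 6.1.8.1 |
|---|---|---|---|
| Grade | 4 or 5 | 4 | 4 or 5 |
| Relatedness and other-cause test | none | none | both |
| Hematologic rule | 14-day platelet/ANC recovery | same as 1.2 | 42-day hypocellular pancytopenia, <5% blasts |
| AML-list events exempt | yes | yes (Appendix F) | yes (Appendix F) |
| Disease-caused cytopenia exempt | yes | yes | yes |

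The conflict is confined to the first three rows. Appendix F includes neutropenia, anemia, thrombocytopenia, infection and bleeding, so much severe toxicity in this population is exempt under every version.

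**2. Constructed subjects on whom the sections disagree**

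- (a) A grade 4 non-hematologic event outside Appendix F, judged unrelated, is a DLT under 1.2 and 5.1 but not under 6.1.8.1. If the event also stops dosing before 80% of Cycle 1, the subject is an evaluable DLT under 5.1 but, under 6.1.8.1, a non-evaluable subject who may be replaced. The denominator changes too.
- (b) A related grade 5 non-hematologic event outside Appendix F with no other clear cause is a DLT under 1.2 and 6.1.8.1, but not on the literal wording of 5.1.
- (c) Leukemia-free marrow, last venetoclax dose on Day 28, platelets and ANC below both thresholds from Day 15, still low on Day 42 and recovered on Day 50. Duration is 49 − 15 + 1 = 35 days, which is under 42. This is a DLT under 1.2 and 5.1 but not under 6.1.8.1.

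**3. Timing of the 42-day rule**

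With inclusive days, onset on Day d completes on Day d + 41. Cytarabine starts on Day 1 (Table 4), and both SAPs count it as study drug, so onset can be as early as Day 1.

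- Onset Day 1: 1 + 41 = Day 42, which is 14 days past Day 28.
- Onset Day 28: 28 + 41 = Day 69, which is 41 days past Day 28.

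The typical decision time for the last subject runs to 28 + 14 = Day 42. The readout therefore falls 42 − 42 = 0 to 69 − 42 = 27 days after the upper end. Subjects enrolled earlier in the cohort have longer follow-up.

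**4. Timing of the 14-day rule**

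Section 6.1.8.3 holds venetoclax from Day 28 in a subject with a leukemia-free marrow and grade 4 neutropenia or thrombocytopenia. Taking Day 28 as the last dose, readout is 28 + 14 = Day 42, also outside Cycle 1. Otherwise venetoclax runs daily into Cycle 2. With no hold there is no last dose in Cycle 1 from which to start the clock.

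**5. What one subject can do**

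- Six subjects: 1/6 = 16.7% clears; 2/6 = 33.3% does not.
- Table 3 of the efficacy SAP gives 92 subjects overall and 82 at 600 mg, so 92 − 82 = 10 at 800 mg. If all 10 counted, 3/10 = 30% clears and 4/10 = 40% does not. The evaluable number is not given.

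**6. Sensitivity under assumed DLT rates**

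The documents give no rates. For a 3 + 3 level with true DLT rate p and q = 1 − p, the probability of escalating is q³ + 3pq² × q³. This is 0.906 at p = 10%, 0.814 at 15%, 0.709 at 20% and 0.600 at 25%. If the broader definition added 5, 10 or 15 points to a 10% rate, the probability would fall by 9, 20 or 31 points.

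**The case against.** Several points weigh on the other side.

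- **Section 6.1.8.1 is headed as the definition, so it governs.** This is implied only. Section 5.1 is equally definitional and is attached to the escalation rules. The closing sentence of 6.1.8.1 that points back to its own definition concerns continued dosing of individual subjects.
- **The times can be reconciled.** Counted from the start of Cycle 1, 42 days equals 28 + 14, which matches both the 14-day rule after a Day 28 last dose and the upper decision time. This is plausible and may be what was meant, but the text says lasting, not counted from Day 1. Even on that reading the two criteria measure different things.
- **Late events are not lost.** Section 6.1.8.1 allows them to be considered, and Section 5.1 says that "adverse events occurring after Cycle 1 in previous dose levels and ongoing PK assessments may inform dose escalation decisions". This softens the timing problem, but by discretion rather than rule.
- **The grade 5 gap is probably a drafting slip.** Two of the three sections name grade 5. Under Section 6.1.2 an event that worsens is re-reported at its new grade, so a fatal toxicity that passed through grade 4 would meet 5.1 anyway. This stands, and little weight rests on example (b).
- **The wording in force is not shown.** Section 6.1.8.2 indicates that escalation ran under Version 1 and Amendment 1. Those texts and the interim study reports are not available here and may settle the matter.

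A reader might infer that only the 42-day rule misses the window; the 14-day rule has the same fault. A reader might also infer that any reported MTD is uninterpretable, or that 600 mg was the wrong dose. The documents support neither. They contain no DLT counts, and Section 6.1.8.7 also uses the types of DLTs, or safety and PK data if no MTD is reached.

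**Conclusion.** The inconsistency is real and should be fixed. The current protocol conflicts on relatedness and other-cause attribution and on the hematologic criterion, and it states no precedence. It therefore does not identify the definition behind the DLT count and MTD. Read literally, neither hematologic rule can be completed within the 4-week window.

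The size is one subject's classification at a decision boundary: 1/6 versus 2/6, or 3/10 versus 4/10 on the assumption that all 10 subjects at 800 mg were counted. The example subjects are constructed, and no actual misclassification is shown. Enrolment is complete, so no escalation decision changes, and the efficacy endpoints are unaffected.

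**What to change.** State one governing DLT definition that covers grade 4 or 5, relatedness, and a single hematologic rule with a fixed anchor and readout day. One option is platelet and ANC recovery by Day 42, counted from Cycle 1 Day 1, in a subject with leukemia-free marrow, whether or not venetoclax was held.

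State which definition was applied during escalation. Report DLT counts and any MTD for evaluable Phase 1 subjects under that definition, with a sensitivity table under the other written definition from existing data. Mark subjects as not assessable where the record is missing. Marrow cellularity may be absent because core biopsy is optional at some sites (Section 5.3.1.1). An alternative cause is required only for serious events (Sections 6.1 and 6.1.4).

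The cost is a clarification in the protocol or study report and one extra table. The downsides are some non-assessable subjects and a DLT count that may rise.

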6.1.8.2 Prophylaxis and Management of Tumor Lysis Syndrome (TLS)

There is a potential for TLS for patients with AML receiving induction therapy, especially for those with elevated pretreatment LDH levels, elevated leukocyte count, renal dysfunction, and dehydration. To mitigate the risk for TLS,³⁶ subjects will receive tumor lysis prophylaxis, including hydration (e.g., oral, intravenous) and treatment with an agent to reduce the uric acid level (e.g., allopurinol, rasburicase).^{36,41}

TLS prophylaxis must be initiated in all such subjects prior to the first venetoclax dose or first new escalated dose.

Tumor Lysis Syndrome Prophylaxis and Management for Subjects Dose Escalated in Protocol Version 1 and Amendment 1

- Hospitalization recommended on Day –1 and mandated by Day 1 and for a minimum of 24 hours after any venetoclax dose escalation.
- Nephrology (or other acute dialysis service) should be available on each admission per institutional standards to ensure emergency dialysis is available.
- An agent to reduce the uric acid level (e.g., allopurinol) to be initiated at least 24 hours prior to venetoclax dosing. Treatment may need to be continued for up to 28 days based on the ongoing risk of TLS development. Subjects allergic to allopurinol must use another uric acid reducer starting at least 24 hours prior to venetoclax dosing or rasburicase on the day of treatment (prior to venetoclax dosing).
- Oral hydration (at least 1 to 2 liters) starting from at least 24 hours prior to first venetoclax dose or any dose escalation.
- Intravenous hydration (target 150 to 200 mL/hr, as tolerable) must be started upon admission and continued during hospitalization as appropriate. Urine output must be monitored.

- Chemistries on the first day of venetoclax dosing at 0 (within 4 hours prior to dosing), 4, 8 and 12 hours and each day of a new dose at 0 (within 4 hours prior to dosing), 4, 8 and 12 hours.*
- Chemistries at 24, 48, 72 hours after receiving the first designated target dose.*
- Collection of samples for venetoclax PK assay 8 hours after dosing on each day of new dose. The 8-hour post-dose PK sample may be collected up to 1 hour earlier or up to 20 minutes after the scheduled time, if necessary to facilitate sample processing.

* Chemistry samples (calcium, inorganic phosphorus, potassium, uric acid, and creatinine) must be reviewed by the investigator real time and prior to the subject's next dose to ensure appropriate subject management. Based upon the results, subjects may need further monitoring or may need additional post-dose labs. Refer to [Appendix E](#) (Recommendations for Initial Management of Electrolyte Imbalances and Prevention of Tumor Lysis Syndrome [TLS]) and [Appendix H](#) (Tumor Lysis Syndrome Classification) for toxicity management guidelines and procedures to follow for TLS prevention. If a subject meets criteria for clinically significant laboratory or clinical TLS, no additional venetoclax doses should be administered until resolution.

Refer to [Table 10](#) (footnote "a") for a special sample handling procedure that must be followed to avoid ex vivo uric acid degradation in the presence of rasburicase.

Drug interruption for up to 72 hours following transient (i.e., lasting < 48 hours) chemical changes and laboratory TLS may be allowed and will not require a dose reduction. If the TLS has not resolved within 72 hours, then a dose reduction should be considered.

If TLS requires a dose hold or dose modifications, after resolution of electrolyte imbalances ([Appendix E](#)), venetoclax may be continued at the same dose per discussion between the investigator and the AbbVie medical monitor.

Tumor Lysis Syndrome Prophylaxis and Management in Phase 2 Cohort C – Applies to Subjects Enrolled in Amendment 2

Safety data from the 94 subjects treated in 3 AML studies demonstrated no events of clinical TLS; 40 subjects treated in the escalation phase of this study; 32 subjects in monotherapy study (Study M14-212) and 22 subjects in a combination study (Study M14-387) using low dose cytarabine. Based on this data, simplification of TLS prophylaxis and management will be followed for subjects enrolled into Cohort C.

All subjects enrolled into Phase 2 Cohort C will need TLS prophylaxis and monitoring. Below are the minimum requirements for TLS prophylaxis and management for subjects enrolled into the expansion phase. All other prophylaxis and monitoring procedures for TLS will be done as per institutional/regional standards:

- All subjects will be hospitalized on or before Day 1 of Cycle 1 prior to administration of the initial dose of study treatment and remain in the hospital at least for 24 hours after reaching the final dose of venetoclax. TLS chemistry tests should be confirmed 24 hours after reaching the maximal dose of venetoclax.
- Administration of uric acid reducing agent, adequate oral and intravenous hydration while monitoring the fluid status of the subject prior to and during the ramp-up of venetoclax will be based on regional standards or institutional guidelines.
- Tumor Lysis Syndrome chemistry tests to be drawn (calcium, inorganic phosphorus, potassium, uric acid, and creatinine) on the first day of venetoclax dosing and each day of a new dose at 0 (within 4 hours prior to dosing) and 6 – 8 hours post dose.* Additional laboratory assessments may be performed, per investigator discretion, post-dose during ramp-up and up to 48 hours after reaching final dose if clinically indicated.
- Abnormal chemistry tests should be corrected promptly.
- If a subject meets criteria for clinically significant laboratory or clinical TLS, no additional venetoclax dose should be administered until resolution.
 - Prophylactic reductions of potassium, inorganic phosphorus and/or uric acid above normal range are recommended prior to beginning study treatment and continue based on the ongoing risk of TLS.

* Chemistry samples (calcium, inorganic phosphorus, potassium, uric acid, and creatinine) must be reviewed by the investigator real time and prior to the subject's next dose to ensure appropriate subject management. Based upon the results, subjects may need further monitoring or may need additional post-dose labs. Refer to [Appendix E](#) (Recommendations for Initial Management of Electrolyte Imbalances and Prevention of Tumor Lysis Syndrome [TLS]) and [Appendix H](#) (Tumor Lysis Syndrome Classification) for toxicity management guidelines and procedures to follow for TLS prevention. If a subject meets criteria for clinically significant laboratory or clinical TLS, no additional venetoclax doses should be administered until resolution.

For continued dosing of venetoclax, monitor for evidence of TLS during treatment, and manage abnormalities in serum creatinine, uric acid and electrolytes promptly. For subjects at higher risk (e.g., circulating blasts), more intensive measures should be considered.

Refer to [Table 10](#) (footnote "a") for a special sample handling procedure that must be followed to avoid ex vivo uric acid degradation in the presence of rasburicase.

Drug interruption for up to 72 hours following transient (i.e., lasting < 48 hours) chemical changes and laboratory TLS may be allowed and will not require a dose reduction. If the TLS has not resolved within 72 hours, then a dose reduction should be considered.

